We plan to use a Bayesian analysis of the evolving data which allows flexibility in the number and timing of the interim analyses. If we determine there is  $>95\%$  probability of the odds ratio being  $>1.0$ , the DSMB should consider stopping the trial for efficacy. If we determine there is  $>90\%$  probability that the odds ratio is  $<1.1$ , the DSMB should consider stopping the trial for futility. If we determine there is  $>70\%$  probability that the odds ratio is  $<0.70$ , the DSMB should consider stopping the trial for harm. We will use a prior odds ratio of 1.0 (equal chance of harm and benefit; mean log OR of 0.0) and a prior distribution of the standard error for its log set at 0.352 for tests of efficacy and a non-informative prior for tests of futility and harm. The results will be reported in a similar manner to those published by Goligher et al. One advantage of Bayesian analysis is that stopping guidelines are not binding and the DSMB is charged with using judgement and data both internal and external to the trial to make any irrevocable decision.

If the trial enrolls 30 participants, further enrollment will be paused until the DSMB reviews data on the primary outcome from all enrolled participants; a decision to continue enrollment will be made by the DSMB while the investigators remain blinded.

Stopping points:

We will conduct a futility analysis at 20 patients. If no efficacy is observed or the primary endpoint indicates worse outcomes, the study will be halted.

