## **9.2 Minimization of Risk**

Federal regulations at 45 CFR 46.111(a)(1) require that risks to participants are minimized by using procedures which are consistent with sound research design. This trial protocol incorporates numerous design elements to minimize risk to patients that meet this human subject protection requirement. Magnesium citrate has been approved by the Food and Drug Administration and has been used in clinical practice for decades in a number of patient populations with an established safety profile. The dose and route of administration of magnesium citrate and the probiotic Floranexs in this trial are comparable to the dose and route of administration approved for uses already approved by the FDA. The trial protocol includes on-study monitoring to minimize the risk to patients during therapy. This monitoring also includes both automated electronic health record and manual study personnel review for medications with potential interactions with magnesium citrate and the probiotic Floranexs. The trial protocol includes monitoring of adverse events, clinical outcomes, and interim analyses by an independent data and safety monitoring board empowered to stop or modify the trial at any time.

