## **12. DATA AND SAFETY MONITORING BOARD (DSMB)**

The principal role of the DSMB is to assure the safety of participants in the trial. They will regularly monitor data from this trial, review and assess the performance of its operations, and make recommendations to the steering committee with respect to:

- Review of adverse events
- Interim results of the study for evidence of efficacy or adverse events
- Possible early termination of the trial because of new external information, early attainment of study objectives, safety concerns, or inadequate performance
- Possible modifications in the clinical trial protocol
- Performance of individual centers

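### For the 20-patient look, Section 7.1 sets non-binding numeric guidelines and also a mandatory halt with undefined terms, and the two can disagree on the same data

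*Combined protocol and SAP*

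**What the plan says.** Section 7.1 assumes an interim look about every ten patients, so the Bayesian guidelines apply at 20. For futility, if the posterior probability that the odds ratio (OR) is below 1.1 exceeds 90%, "the DSMB should consider stopping the trial for futility". For harm, the trigger is a probability above 70% that the OR is below 0.70. Both use "a non-informative prior for tests of futility and harm". The efficacy guideline is a probability above 95% that the OR exceeds 1.0, with "a prior distribution of the standard error for its log set at 0.352 for tests of efficacy". On the standing of all three, the section says that "stopping guidelines are not binding and the DSMB is charged with using judgement".

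Under the label for stopping points, the same section adds "We will conduct a futility analysis at 20 patients", followed by "If no efficacy is observed or the primary endpoint indicates worse outcomes, the study will be halted". No other section connects this pair of sentences to the guidelines.

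**The concern.** The guidelines are numeric and advisory. The added sentence is mandatory and has no number. Absence of efficacy could mean that the futility guideline is met, or that the estimate is not above 1. Worse outcomes could mean that the harm guideline is met, or that the estimate falls on the wrong side of 1. The same 20-patient data can therefore end the trial under one sentence and let it continue under the other. Unless the reading is fixed beforehand, it can be chosen once the data are known. The look comes two-thirds of the way to 30 patients, so the chance that a useful treatment is dropped there matters.

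**Working it through.** **Inputs.** 20 patients allocated 1:1, about 10 per arm. Thresholds and priors are those of Section 7.1. The outcome mix is Table 1: 11.5%, 5.8%, 21.9%, 60.8%. (The text gives 22.9% where the table has 21.9%; using the text moves the SE below only to 0.881.) The plan prints no SE, target OR, power or chance of stopping, so it has no figure to reproduce. The SE is an assumption.

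**Step 1, SE of log OR.** For a proportional odds model with 1:1 allocation, SE = √(12 / (N·K)), with K = 1 − Σp³ = 1 − (0.0015 + 0.0002 + 0.0105 + 0.2248) = 0.763.
- N = 20: √(12 / 15.26) = 0.887.
- N = 30: √(12 / 22.89) = 0.724. The plan says it calculated this quantity but does not give it.

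**Step 2, observed OR at which each reading halts.** With a flat prior the posterior for log OR is normal, centred on the estimate.
- Futility guideline: ln 1.1 − 1.2816 × 0.887 = −1.041, an observed OR below 0.35.
- Harm guideline: ln 0.70 − 0.5244 × 0.887 = −0.822, an observed OR below 0.44. This bound is the looser of the two, so it also serves for futility or harm.
- Observed OR of 1 or less: bound 0.

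**Step 3, chance of a halt**, Φ((bound − ln OR) / SE):

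| Reading | True OR 1 | True OR 2 |
|---|---|---|
| Futility guideline | Φ(−1.174) = 12.0% | Φ(−1.956) = 2.5% |
| Futility or harm guideline | Φ(−0.927) = 17.7% | Φ(−1.708) = 4.4% |
| Observed OR ≤ 1 | Φ(0) = 50% | Φ(−0.782) = 21.7% |

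**Step 4, disagreement.** The third reading halts while neither guideline is met in 50.0 − 17.7 = 32.3% of trials at OR 1, and in 21.7 − 4.4 = 17.3% at OR 2.

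**Step 5, simulation.** At OR 1, 4,000 trials of 10 per arm with an unadjusted proportional odds fit gave 11.5% (futility), 18.4% (futility or harm) and 48% to 52% (observed OR below 1, or at most 1). At OR 2, 500 fitted trials gave 1.9% for futility and 23.9% for an observed OR of 1 or less. The latter lies between 22.6% and 28.2% once the 28 fits without a usable estimate are counted either way.

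**Step 6, other SEs.** Each cell is the chance of a halt at OR 1 / OR 2.

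| SE | Futility | Futility or harm | Observed OR ≤ 1 |
|---|---|---|---|
| 0.775 (K = 1, most information possible) | 12% / 2.0% | 16% / 3.0% | 50% / 19% |
| 1.2 to 1.5 times 0.887 (assumed cost of covariate adjustment) | 11–12% / 3–4% | 20–21% / 7–9% | 50% / 26–30% |

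**Step 7, enrolment at OR 1** with this look as the only stop before the pause at 30, 30 − 10 × P(halt): 28.8, 28.2 and 25.0 patients for the three readings.

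**The case against.** The strongest defence is context. The mandatory sentence directly follows one announcing a futility analysis, and futility already has a definition a few lines above. Harm has one too, and it fits the phrase about worse outcomes. On that view the sentence only schedules the existing guidelines, and the chance of a halt at OR 1 is 12% to 18%. This is a fair reading and may be what was meant. It narrows the numerical spread but does not remove the conflict. The sentence would still order a halt where the guidelines ask only for consideration, and nothing in the text rules out the plain reading that an estimate not above 1 ends the study.

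Three stronger inferences are tempting, and the documents do not support them.

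- **The halt ends nearly every trial.** A reader might take absence of efficacy to mean that the 95% efficacy criterion is not met. With 0.352 read as the prior SD of log OR, avoiding a halt needs a log OR estimate above 1.645 × √(1.272 + 8.071) / 1.272 = 3.95, where 1.272 = 1/0.887² and 8.071 = 1/0.352². The halt then occurs in over 99% of trials at OR 1 and OR 2. But Section 7.1 assigns that prior to efficacy tests and calls this look a futility analysis, for which it specifies a non-informative prior. Under a flat prior the same reading halts Φ(1.645) = 95% at OR 1 and Φ(1.645 − 0.782) = 81% at OR 2. Either version would leave the planned review at 30 patients with little purpose. This is a sensitivity case only.
- **No 20-patient result could escape a halt under the 0.352 prior.** This is not general. Where every treated patient does better than every control, the posterior probability of benefit in one example ranges from about 0.91 to 0.96, depending on where the prior on the outcome categories is anchored. The plan does not specify that.
- **No one is named to decide.** The halt sentence itself names no one, but Section 7.1 leaves irrevocable decisions to the DSMB, and Section 9.2 describes an "independent data and safety monitoring board empowered to stop or modify the trial at any time". Section 12, under which the DSMB will "make recommendations to the steering committee with respect to" such matters, is ordinary charter wording.

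**Conclusion.** The concern holds as a conflict within one decision rule, and it should be resolved before the 20-patient look. Between the plan's own futility threshold and the plain reading, the chance of a halt moves from 12% to 50% for an inert treatment and from 2.5% to 22% at a true OR of 2. These figures rest on a normal approximation, on an SE borrowed from Table 1, on an unadjusted model although five covariates are planned, and on a single look with no earlier stop. The gap between readings persists across the SEs tried. The textual conflict does not depend on any of these numbers.

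**What to change.** Before the 20-patient look, reconcile Section 7.1 into one rule. Two forms would do, and the choice belongs to the trial team:

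1. Delete the mandatory sentence and write: *At 20 patients the DSMB reviews the futility and harm guidelines above, which remain non-binding.*
2. Keep the halt, state its criterion on the OR scale together with its prior, and say that the statement about guidelines not binding the DSMB does not apply to this look.

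No criterion is proposed here. Under whichever rule is chosen, report the chance of stopping at 20 for a true OR of 1 and for at least one beneficial OR.

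The editing cost is one or two sentences and a small table. Relying on the existing guidelines rather than an observed OR of 1 or less enrols on average 28.2 − 25.0 = 3.2 to 28.8 − 25.0 = 3.8 more patients when the treatment does nothing. Keeping the broader halt costs about 22% of trials at a true OR of 2.

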## **7.2 Planned deviations from this design**

This trial is being conducted in a rapidly evolving pandemic of a novel disease. Thus, we have developed a statistical plan with flexibility to be modified based on results from other concurrently conducted trials and emerging data on the clinical epidemiology of COVID-19. The primary advantage of a Bayesian monitoring plan is that whenever the trial is stopped the inference only depends on the data and not the original statistical plan that was developed at a time when less was known about COVID-19 and potentially effective treatments.

## **8. DATA QUALITY MONITORING AND STORAGE**

### **8.1 Data Quality Monitoring**

Data quality will be reviewed remotely using front-end range and logic checks at the time of data entry and back-end monitoring of data using application programming interface tools connecting the online database to statistical software to generate data reports. Patient records and case report forms will also be examined by site personnel for a randomly selected 5-10% sample to evaluate the accuracy and completeness of the data entered into the database and monitor for protocol compliance. The coordinating center will perform remote monitoring of each study site to examine the completeness and accuracy of informed consent documents for study participants, documentation of eligibility criteria, and the completeness of study outcome collection.

### **8.2 Data Storage**

Data will be entered into a secure online database. All data will be maintained in the secure online database until the time of study publication. At the time of publication, a de-identified version of the database will be generated.

## **9. RISK ASSESSMENT**

### **9.1 Potential Risk to Participants**

Although both magnesium citrate and the probiotic Floranex are FDA approved medications with an established safety profile, potential risks exist to participating in this study of magnesium citrate plus the probiotic Floranex versus placebo for the treatment of COVID-19. Mild hypermagnesemia (increases of >1meq) are typical because the majority of the medication remains intraluminal. Patients with renal insufficiency (<30cc/min) are at risk for greater increases in systemic magnesium levels and thus they will be excluded from study participation. Below, we outline side effects based on serum magnesium levels.

#### **9.1.1 Potential risks of receiving magnesium citrate**

Common Side effects of magnesium citrate include:

Abdominal cramping

Diarrhea

Electrolyte imbalance

Gas (flatulence)

Nausea

Vomiting

Hypermagnesemia (high levels of magnesium in the blood).

Side effects that can occur with Hypermagnesemia:

Nervous system

- Muscle weakness, decrease in tendon reflexes, mental confusion, or sedation when serum magnesium (Mg) levels increase to 4 to 7 mEq/L,
- Slowed respiratory rate and hypotension when serum magnesium (Mg) levels increase to 5 to 10 mEq/L

- Profound mental depression, areflexia, coma and respiratory paralysis when serum Mg levels increase to 10 to 15 mEq/L
- Death possible when serum Mg levels rise to 15 mEq/L or higher.

#### Cardiovascular

- Hypotension may be observed when serum Mg levels rise to 5 to 10 mEq/L.
- Hypotension, depressed myocardial conductivity, and bradyarrhythmias may be associated with levels greater than 10 mEq/L.
- Asystole when levels rise to 25 mEq/L.

#### Metabolic

- Hypocalcemia

#### Gastrointestinal

- Nausea when serum Mg levels rise to 4 to 5 mEq/L.
- Rare cases of paralytic ileus associated with serum Mg levels greater than 5 mEq/L have been reported.
- 

### **9.1.2 Potential risks of receiving the probiotic Floranexs**

Risks include is gas, bloating and diarrhea.

### **9.1.3 Potential risks of receiving placebo with COVID-19**

One potential risk to participating in this study is receiving placebo rather than magnesium citrate plus the probiotic Floranex. This risk is only relevant if magnesium citrate plus the probiotic Floranex is ultimately found to be an effective therapy for COVID-19 and is not relevant if magnesium citrate plus the probiotic Floranex is ultimately found to be an ineffective therapy for COVID-19. This trial protocol minimizes this risk through rigorous design to minimize the number of patients who must be enrolled to determine whether magnesium citrate plus the probiotic Floranex is an effective therapy for COVID-19, excluding patients who decline to participate because they feel their optimal care requires magnesium citrate plus the probiotic Floranex, excluding patients whose treating clinicians declines to allow enrollment because they feel the patient's optimal care requires treatment with magnesium citrate plus the probiotic Floranex, and specifying procedures for stopping the study drug, unblinding, and allowing open-label administration of magnesium citrate plus the probiotic Floranex for patients who experience clinical deterioration during the study period.

## **9.2 Minimization of Risk**

Federal regulations at 45 CFR 46.111(a)(1) require that risks to participants are minimized by using procedures which are consistent with sound research design. This trial protocol incorporates numerous design elements to minimize risk to patients that meet this human subject protection requirement. Magnesium citrate has been approved by the Food and Drug Administration and has been used in clinical practice for decades in a number of patient populations with an established safety profile. The dose and route of administration of magnesium citrate and the probiotic Floranexs in this trial are comparable to the dose and route of administration approved for uses already approved by the FDA. The trial protocol includes on-study monitoring to minimize the risk to patients during therapy. This monitoring also includes both automated electronic health record and manual study personnel review for medications with potential interactions with magnesium citrate and the probiotic Floranexs. The trial protocol includes monitoring of adverse events, clinical outcomes, and interim analyses by an independent data and safety monitoring board empowered to stop or modify the trial at any time.

### **9.3 Potential Benefit**

Study participants may or may not receive any direct benefits from their participation in this study. Administration of magnesium citrate plus the probiotic Floranex may improve clinical outcomes among adults hospitalized for COVID-19 infection.

### **9.4 Risk in Relation to Anticipated Benefit**

Federal regulations at 45 CFR 46.111 (a)(2) require that “the risks to subjects are reasonable in relation to anticipated benefits, if any, to subjects, and the importance of the knowledge that may reasonably be expected to result.” Based on the preceding assessment of risks and potential benefits, the risks to subjects are reasonable in relation to anticipated benefits.

## **10. HUMAN SUBJECTS PROTECTIONS**

Each study participant or a LAR must sign and date an informed consent form. Approval of the central institutional review board will be required before any participant is entered into the study.

### **10.1 Selection of Subjects**

Federal regulations at 45 CFR 46(a)(3) require the equitable selection of subjects. The Vanderbilt University Medical Center emergency departments, hospital wards, and ICUs will be screened to determine if any patient meets inclusion and exclusion criteria. Data that have been collected as part of the routine clinical care of the patient will be reviewed to determine eligibility. If any patient meets criteria for study enrollment, then the attending physician responsible for his or her care will be asked for permission to approach the patient or his or her LAR for informed consent. Study exclusion criteria neither unjustly exclude classes of individuals from participation in the research nor unjustly include classes of individuals for participation in the research. Hence, the recruitment of participants conforms to the principle of distributive justice.

### **10.2 Justification of Including Vulnerable Subjects**

The present research aims to investigate the safety and efficacy of magnesium citrate plus the probiotic Floranex for the treatment of patients with COVID-19 who are at high risk for respiratory failure and mortality. Due to the nature of this patient population, many of these patients will have impaired decision-making capabilities. Moreover, those with intact decision-making capacities probably have milder disease than those with impaired capacity. Therefore, the validity of the study and its generalizability to severely ill patients would be compromised by enrolling only those participants with retained decision-making capacity. Hence, participants recruited for this trial are not being unfairly burdened with involvement in this research.

### **10.3 Informed Consent**

Federal regulations 45 CFR 46.111(a)(5) require that informed consent will be sought from each patient or the patient’s LAR. Study personnel obtaining informed consent are responsible for ensuring that the patient or LAR understands the risks and benefits of participating in the study, answering any questions the patient or LAR may have throughout the study and sharing any new information in a timely manner that may be relevant to the patient’s or LAR’s willingness to permit the patient’s continued participation in the trial. The study personnel obtaining informed consent will make every effort to minimize coercion. All patients or their LARs will be informed of the objectives of the study and the potential risks. The informed consent document will be used to explain the risks and benefits of study participation to the patient or LAR in simple terms before the patient is entered into the study, and to confirm that the patient or LAR is satisfied with his or her understanding of the risks and benefits of participating in the study and desires to participate in the study. The investigator is responsible for ensuring that informed consent is given by each patient or LAR. This includes obtaining the appropriate signatures and dates on the informed consent document prior to the performance of any protocol procedures including administration of study agent.

For additional details, see Section 3.

## **10.4 Continuing Consent**

Patients for whom consent was initially obtained from a LAR, but who subsequently regain decision-making capacity while in hospital will be approached for consent for continuing participation, including continuance of data acquisition. The consent form signed by the LAR should reflect that such consent should be obtained. The process for obtaining consent from these patients will be the same as that outlined in section 3.

## **10.5 Withdrawal of Consent**

Participating patients may withdraw or be withdrawn (by the LAR, treating physician, or investigator) from the trial at any time without prejudice. Data recorded up to the point of withdrawal will be included in the trial analysis, unless consent to use data has also been withdrawn. Withdrawal of consent prior to receipt of study drug will constitute a screen-failure and will be recorded. Withdrawal of consent after randomization and administration of one or more doses of study drug will lead to discontinuation of study interventions but site staff will request access to medical records for data related to the trial.

## **10.6 Identification of Legally Authorized Representatives**

Many of the patients approached for participation in this research protocol will have impaired decision-making capacity due to critical illness and will not be able to provide informed consent. Accordingly, informed consent will be sought from the patient's LAR.

Regarding consent from the LAR, the existing federal research regulations ('the Common Rule') states at 45 CFR 46.116 that "no investigator may involve a human being as a subject in research...unless the investigator has obtained the legally effective informed consent of the subject or the subject's legally authorized representative"; and defines at 45 CFR 46 102 (c) a LAR as "an individual or judicial or other body authorized under applicable law to consent on behalf of a prospective subject to the subject's participation in the procedures(s) involved in the research." The Office of Human Research Protections (OHRP) defined examples of "applicable law" as being state statutes, regulations, case law, or formal opinion of a State Attorney General that addresses the issue of surrogate consent to medical procedures. Such "applicable law" could then be considered as empowering the LAR to provide consent for participant participation in the research. Interpretation of "applicable law" may be state specific and will be addressed by the central IRB.

According to a previous President's Bioethics Committee (National Bioethics Advisory Committee (NBAC)), an investigator should accept a relative or friend of the potential participant who is recognized as an LAR for purposes of clinical decision making under the law of the state where the research takes place. Finally, OHRP has stated in their determination letters that a surrogate could serve as a LAR for research decision making if such an individual is authorized under applicable state law to provide consent for the "procedures" involved in the research study

